Clinic staff referred potentially eligible patients who were interested in learning more about the study to a research assistant. During pre-visit wait time, the research assistant explained the study, obtained written caregiver consent and adolescent assent, and administered an eligibility screener. Children were eligible if they were: ages 11 to 17 years; spoke and read English or Spanish; had persistent asthma; were present for an acute or follow-up asthma visit or a well-child visit; and had previously visited the clinic at least once for asthma. Adolescents' caregivers were eligible if they were at least 18 years of age, spoke and read English or Spanish, and were the legal guardian of the adolescent. The research assistant recorded the reasons why individuals declined to participate.

The study statistician prepared the randomization envelopes for the research assistants to use. Adolescents were randomized within providers and opaque envelopes were prepared for the research assistants at each site. A group of envelopes was prepared for each enrolled provider. Eligible adolescents of participating providers were then randomized to the intervention or usual care group. Adolescents in the intervention group watched the video with their caregivers on an iPad. Depending on the clinic, they either watched it in a private area before the visit or they watched it with earphones in the waiting area. The adolescents then received the one-page asthma question prompt list to complete before their visits. Providers were blinded to the adolescent's group assignment. All adolescents' visits were audio-tape recorded. All adolescents were interviewed at baseline after their medical visits by a research assistant while their caregivers completed questionnaires. Research assistants reviewed the caregiver questionnaires before

families left the clinics to ensure data quality. The project manager traveled to the clinics regularly to pick up and review data to ensure quality. Adolescents and caregivers each received \$25 for their time.

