Study outcomes: Our primary outcomes were (a) asthma control, (b) adolescent asthma management self-efficacy, and (c) asthma quality-of-life at 12 months. Asthma control was measured using the 5-item Asthma Control Test which is a valid and reliable measure of asthma control. Using a 5-point Likert scale, responses are summed to indicate a score ranging from 5 (poor asthma control) to 25 (complete asthma control). Scores above 19 are considered "well controlled", 16 to 19 are considered not well controlled, and scores 15 or below are considered "very poorly controlled." Studies have shown the Asthma Control Test to be reliable, valid, and responsive to temporal changes in asthma control. We measured asthma as being controlled if adolescents scored above 19 on the Asthma Control Test. Adolescent asthma management self-efficacy was measured as a summary score using a 14-item scale that has been shown to have a reliability of 0.87. Prior work in asthma has found asthma management self-efficacy to change in response to an intervention. Adolescent quality-of-life was measured as a mean score on the standardized version of the Juniper pediatric asthma quality-of-life questionnaire. The questionnaire contains 23 items organized in three domains: symptoms, activities, and emotional impact of asthma, and has a reliability of 0.84.

Data collection and sources: After enrollment at baseline, caregivers completed a contact information sheet that contained information on the date of initial contact, the caregiver's name and contact information, including postal address, home/cell number, email address and alternative contact information. The research assistant kept in contact with the patient to determine when their 6- and 12-month follow-up visits would occur. The research assistant called first; if the research assistant could not speak to the caregiver directly she would leave a voice message (caregiver was always asked for permission to leave voice messages during initial meeting). If the research assistant did not hear back from the caregiver within a couple of days she would proceed to text, send an email and/or mail a letter. The research assistant would reach out to the alternative contact as the last resort.

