Sample Size Calculations: Our planned enrollment was 360 adolescents. We expected a 20% attrition rate over 12 months based on our prior work. Assuming the same attrition rate, 288 patients, or about 144 patients each in the experimental and usual care groups, would complete the study. We expected to go from 50% of the adolescents in the intervention group being well controlled according to the Asthma Control Test at baseline to 70% of adolescents in the intervention group being well controlled at 12 months. An intervention study conducted with adults with asthma found that an educational intervention increased the percent of adults controlled according to the Asthma Control Test from 50% to 65% over a 6-month period. From past studies, we expected an average self-efficacy score of around 3.7 to 3.8 and average quality of life scores of 5.7 to 5.8 for the adolescents. With 143 families in each group and an expected increase of 20% in asthma control, as well as an expected increase in adolescent self-efficacy and adolescent's quality of life by at least one half of a point, which equates to effect sizes of 0.45 to 0.6, the study is powered at 80% with a type I error rate of 5% for each of the between-group differences for these outcome variables. Our estimates for the control group come from our prior work.

Analytical Approach: All analyses were performed using SPSS. Generalized estimating equations, (i.e., the GEE method) were used to analyze the data, which allowed families to be nested within providers. The GEE method was used to detect clinically significant differences in our primary outcome variables: asthma control, adolescent self-efficacy in asthma management, and adolescent quality-of-life. Primary analysis used the 12-month follow-up data. Our multivariable models for the primary outcomes were nested by provider and included several covariates. For all of our models, we examined relevant interaction terms. For scale items that were missing, we imputed missing scale items using overall sample mean scores.

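### Filling missing items with one overall sample mean shrinks the self-efficacy and quality-of-life differences in points when items are skipped at random; own-mean scoring is a cheap improvement (minor)

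*Combined protocol and SAP*

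**What the plan says.** The only missing-data rule is the last sentence of Analytical Approach: "For scale items that were missing, we imputed missing scale items using overall sample mean scores". The documents do not say whether this means each item's own mean or one mean for the whole scale. They give no minimum number of answered items, and do not say whether a wholly blank scale would still be scored.

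Two of the three primary outcomes are multi-item continuous scores, defined under Study outcomes:
- Self-efficacy: "Adolescent asthma management self-efficacy was measured as a summary score using a 14-item scale that has been shown to have a reliability of 0.87".
- Quality of life: "Adolescent quality-of-life was measured as a mean score on the standardized version" of the questionnaire, and "The questionnaire contains 23 items organized in three domains: symptoms, activities, and emotional impact of asthma, and has a reliability of 0.84".

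Sample Size Calculations gives expected levels ("we expected an average self-efficacy score of around 3.7 to 3.8 and average quality of life scores of 5.7 to 5.8") and an expected gain "by at least one half of a point, which equates to effect sizes of 0.45 to 0.6". Analytical Approach then states the aim: "The GEE method was used to detect clinically significant differences in our primary outcome variables".

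**The concern.** A missing item is replaced by a number that does not depend on the adolescent's arm or on how that adolescent answered the rest of the scale. Each such item pulls the two arm means towards each other. Adolescents who answer everything are unaffected, but the average difference between arms is diluted in proportion to the missing share. More participants would not remove this.

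The plan expresses its expected benefit in points and wants to judge whether differences matter clinically, so the size of the point difference is what a reader will use. Under random skipping the error always runs towards no effect. If lower scorers skip more in one arm, it can run either way.

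The concern is confined to self-efficacy and quality of life. No advantage of own-mean scoring is claimed for the Asthma Control Test dichotomised at above 19.

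**Working it through.** **The plan's own figures.** 360 × 0.8 = 288, or 144 per arm, reproduces. With 143 per group and a two-sided 5% test (sidedness is not stated), power is 96.7% at effect size 0.45 and 99.9% at 0.6, so the stated 80% is a floor. That is a separate matter. The plan has no figure for missing items to reproduce.

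**Inputs.** From the documents: difference 0.5 point; effect sizes 0.45 and 0.6, implying SD = 0.5/0.45 = 1.11 and 0.5/0.6 = 0.83; 144 per arm; 14 items at reliability 0.87 and 23 items at 0.84. Assumed: item-missing rates of 2, 5, 10 and 20%, and equal inter-item correlation r = reliability / (k − (k − 1) × reliability), which gives 0.87/2.69 = 0.32 and 0.84/4.52 = 0.19.

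**Random skipping.** Let c be the common fill value. The filled arm mean is (1 − m) × (arm mean) + m × c. The term in c cancels between arms, so the difference is (1 − m) × 0.5. This is the same for item-specific means and for a single scale mean. With unequal missing shares and observed shares a and b, the factor is 2ab/(a + b). For 10% and 2% missing, 0.5 × 2 × 0.90 × 0.98 / 1.88 = 0.469.

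The 95% half-width is 1.96 × SD × √(2/144), which is 0.26 at effect size 0.45 and 0.19 at 0.6. Coverage comes from simulation (3,000 replicates, provider clustering ignored).

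| Items missing (assumed) | Difference, sample-mean fill | Difference, own mean | Shift as share of half-width (0.45 / 0.6) | Coverage, sample-mean fill |
|---|---|---|---|---|
| 2% | 0.49 | 0.50 | 4% / 5% | 95–96% |
| 5% | 0.475 | 0.50 | 10% / 13% | 94–96% |
| 10% | 0.45 | 0.50 | 19% / 26% | 91–93% |
| 20% | 0.40 | 0.50 | 39% / 52% | 77–85% |

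Own-mean scoring covers 95–96% throughout. Under sample-mean fill the SD is multiplied by 0.98, 0.955, 0.91 and 0.82, which is why tests barely change. At effect size 0.45, power is 96.9–97.1% with complete data and 96.2–96.4% at 20% missing.

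**Low scorers skipping in one arm.** Suppose the lower-scoring half of the intervention arm skips 10% of items (14 items, effect size 0.45). The latent SD is √0.87 × 1.11 = 1.036, so the lower half averages 0.798 × 1.036 = 0.827 below its arm mean, that is 0.5 − 0.827 = −0.327 with the control mean set to 0. The pooled observed mean is (0.5 + 0.05 × 0.327)/1.95 = 0.265. The arm mean rises by 0.05 × (0.265 + 0.327) = 0.030, and 0.530/0.5 = 1.06.

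**Other patterns.** The ratios below are to the complete-data difference (simulation, 1,500 replicates, 10% skipping). Ranges run over the settings tried; in the harder-item rows item means are spread ±0.5 to ±1 point.

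| Who or what is skipped | Own mean | Sample mean |
|---|---|---|
| Lower-scoring half, intervention arm | 1.00 | 1.04–1.06 |
| Lower-scoring half, control arm | 1.00 | 0.89–0.91 |
| Below-average answers, intervention arm | 1.08–1.16 | 1.09–1.17 |
| Below-average answers, control arm | 0.84–0.92 | 0.78–0.86 |
| Below-average answers, both arms | 1.00 | 0.95 |
| Half the items carry all the effect; those skipped | 0.94 | 0.90 |
| Half the items carry no effect; those skipped | 1.06 | 1.00 |
| Harder half of items, intervention arm | 1.03–1.06 | 0.97 item-specific; 1.00–1.03 single |
| Harder half of items, control arm | 0.94–0.97 | 0.97 item-specific; 0.92–0.95 single |
| Harder half of items, both arms | 1.00 | 0.95 |

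**The half-answered floor.** At 20% random skipping, the binomial probability that fewer than half the items are answered is 0.24% for 14 items and 0.06% for 23.

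**The case against.** The strongest reply is that the effect may be negligible here. The Participants section says "All adolescents were interviewed at baseline after their medical visits by a research assistant while their caregivers completed questionnaires", interviews were repeated at 6 and 12 months, and the project manager regularly reviewed the data. All of this points to few skipped items. At 1 to 5% missing the loss is only 0.005 to 0.025 point and coverage stays close to nominal. The striking figures need 20% missing, which nothing in the documents supports. This stands, and it is why the point is minor. It does not make the rule sound, and with no reported rate a reader cannot confirm that the loss is small.

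Second, no test changes. The plan also states its benefit as standardised effect sizes, which survive almost intact, and half a point is a sample-size expectation with no decision rule attached. This also stands. The point concerns the reported difference and its interval only.

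Third, own-mean scoring is not uniformly better. It is worse when only no-effect items are skipped, hardly helps when below-average answers are skipped in the intervention arm, and gains nothing over item-specific means when harder items are skipped in one arm. A whole-scale own mean for quality of life also treats the three domains as interchangeable if one is blank. That case was not simulated and falls under the unequal-effects limit. These limits stand.

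Fourth, the simulation omits provider clustering and covariates, unlike the planned GEE models. The coverage and power figures are therefore illustrative. The (1 − m) factor is algebra on arm means and does not depend on clustering.

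**Conclusion.** The concern holds, at minor severity. The stated rule biases the point difference towards zero by the share of items missing, given random skipping at similar rates in both arms; unequal rates still shrink it. Under non-random skipping the bias can take either sign, with factors from 0.78 to 1.17 in the settings tried. The actual missing rate is unknown and probably low, so the likely loss is around a hundredth or a few hundredths of a point. Own-mean scoring removes the bias under random skipping and low-scorer skipping, and reduces or matches it in most, but not all, of the other patterns.

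**What to change.** For self-efficacy and quality of life, replace the sample-mean fill with the adolescent's own mean of answered items on that scale when at least half the items are answered; otherwise treat the scale score as missing. For quality of life, take the own mean over all 23 items, which agrees with its definition as a mean score and stays defined if one domain is blank. The half-answered floor is a proposed choice; the documents do not supply one. The Asthma Control Test may be scored the same way for uniformity, with no gain claimed.

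Report the item-missing rate by arm and by item, so that a reader can see whether any of the patterns where own-mean scoring does not help is present.

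The cost is rescoring from existing item-level data and rerunning the two models, plus the asthma control model if it is scored the same way. The downside is that mostly blank scales become missing outcomes, for which the plan states no method. Under random skipping that would be well under 1% of forms even at 20% missing.
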